# 6.0 STUDY PROCEDURES

#### 6.1 Screening/Baseline Procedures

Assessments performed exclusively to determine eligibility for this study will be done only after obtaining informed consent. Assessments performed for clinical indications (not exclusively to determine study eligibility) may be used for baseline values even if the studies were done before informed consent was obtained.

#### 6.2 Time and Events Table/Schedule of Events/Study Calendar

| Table 4. Study Calendar                       |                        |         |       |         |       |                            |                        |                          |
|-----------------------------------------------|------------------------|---------|-------|---------|-------|----------------------------|------------------------|--------------------------|
| Procedures                                    | Screening  | Cycle 1 |       | Cycle X |       | EOT
Visit  | Follow-Up
Q3 months |                          |
|                                               |                        | Day 1   | Day 8 | Day 15  | Day 1 | Day 15                     | VISIT                  | +/- 1 week  |
| Informed Consent                              | Х                      |         |       |         |       |                            |                        |                          |
| History, Physical
Examination              | Х                      | Х       |       | Х       | Х     |                            | Х                      | Х                        |
| Weight, BSA                                   | Х                      | Χ       |       |         | Х     |                            | Х                      |                          |
| Vital Signs                                   | Х                      | Χ       |       | Х       | Χ     | Х                          | Х                      |                          |
| Performance Status                            | Х                      | Х       |       |         | Х     |                            | Х                      |                          |
| Toxicity
Evaluations          |                        | Х       | Х     | Х       | Х     | X                          | Х                      | Х                        |
| CBC with differential                         | Х                      | Χ       |       | Х       | Χ     | Х                          |                        |                          |
| CMP                               | Х                      | Χ       | Х     | Х       | Х     | Х                          |                        |                          |
| Other labs                        |                        | Х       |       |         | Х     |                            |                        |                          |
| CA 19-9 (or CEA)                  | X                      | Х       |       |         | Х     |                            | Х                      |                          |
| PT, PTT                                       | X                      |         |       |         |       |                            |                        |                          |
| Pregnancy Test⁵                               | X                      | Χ       |       |         | Х     |                            |                        |                          |
| Concomitant
Medication Review              | Х                      | Х       |       |         | Х     |                            |                        |                          |
| Scans with Tumor
Measurements  | Х                      |         |       |         | Х     |                            |                        |                          |
| Research Blood                    |                        | Χ       |       |         | Χ     |                            | Х                      |                          |
| Tissue                            | Х                      |         |       |         | Х     |                            | Х                      |                          |
| Study Drug
Administration      |                        | Х       |       | Х       | Х     | Х                          |                        |                          |
| Survival Follow-up                            |                        |         |       |         |       |                            |                        | Х                        |

1. All screening procedures to be completed within 2 weeks of registration, except imaging and informed consent which should be ≤ 4 weeks. Protocol treatment is to begin ≤14 calendar days of registration.

2. Comprehensive metabolic panel includes BUN/creatinine, sodium, potassium, chloride, glucose, calcium, alkaline phosphatase, AST, ALT, total bilirubin and total protein.

3. Amylase, lipase, random cortisol, TSH, free T4 and T3 on cycle 1 day 1, and then day 1 of every odd numbered cycle.

4. Check CA 19-9 (or CEA, if CA 19-9 not expressed) every 8 weeks, if patient is known to express these tumor markers.

- 5. Required for females of childbearing potential. Blood or urine pregnancy test per site investigator discretion. Required on C1D1 within 24 hours prior to treatment initiation and prior to study drug administration on Day 1 for each subsequent Cycle.
- 6. MRI or CT (abdomen/pelvis) with contrast along with CT chest with/without contrast will be assessed every 8 ± 1 weeks. Imaging assessment of scans at the site should be completed by either a radiologist or an imaging core, and not by the oncologist nor via abstraction of data from the subjective/clinical radiology report.
- 7. Collect 10 ml x 2 Streck® DNA tubes (must be shipped within 48 hours of collection) See Section 10.1 for details. Cycle 1 Day 1 specimens will be collected pre-treatment and Cycle X Day 1 specimens will only be collected on Cycle 3 Day 1 prior to drug administration.
- 8. Pre-treatment, diagnostic pathology specimens obtained in the course of standard biopsy or surgery. Formalin-Fixed Paraffin-Embedded (FFPE) block(s) (preferred), or 20 FFPE slides plus H&E slide is required. Procurement of tissue is mandatory for enrollment. On-treatment biopsies will only be collected for patients enrolled at the University of Michigan. Post-treatment biopsies on progression are optional (see Section 10.1).
- 9. See Section 5.1 for details. Study drug administration with associated labs will have a window of + 3 days.
- 10. End of treatment (EOT) visit should be completed within 30 days of last treatment
- 11. Patients will be followed every 3 months +/- 1 week after completion of (or early withdrawal from) study treatment until death, withdrawal from protocol or 2 years whichever is the earliest.
- 12. Data on adverse events will be collected from the time of the initial study treatment administration through 100 days after the last dose of study treatment. Any serious adverse event that occurs more than 100 days after the last study treatment and is considered related to the study treatment or intervention must also be reported.

#### 7.0 MEASUREMENT OF EFFECT

# 7.1 Antitumor Effect- Solid Tumors

Immunotherapy drugs such as nivolumab can initially cause inflammation in the early stages of treatment. Immune-related RECIST (irRECIST) utilizes RECISTv1.1 but considers an inflammatory response (or "pseudo-progression") as normal. The main difference between RECISTv1.1 and irRECIST is that patients can stay on trial after the first progressive disease (PD) assessment (as per RECISTv1.1) if using immune-related RECIST criteria. This PD per RECISTv1.1 is then re-labeled as immune related stable disease (irSD) per irRECIST and requires addition of unidimensional measurements of all new lesions (that meet the definition of target lesion) to be added to the sum of longest diameters (SLD) calculation for response assessment. Importantly, immune-related progression (irPD) must be confirmed by a follow-up scan at least 4 weeks (within 4-8 weeks) following the initial PD/irSD assessment in order to take the patient off the trial.

Subjects that are deemed to have clinical progression and unstable should not be continued on therapy after PD (per RECISTv1.1) and are therefore not required to have repeat tumor imaging for confirmation as per irPD definition. It is at the discretion of the site investigator whether to continue a subject on study treatment until repeat imaging is obtained. This clinical judgment decision by the site investigator should be based on the subject's overall clinical condition, including performance status, clinical symptoms, and laboratory data.

#### 7.1.1 Definitions

Evaluable for toxicity. All patients will be evaluable for toxicity from the time of their first treatment with study drug.

Evaluable for primary endpoint, PFS at 4 months. All patients that receive at least one dose of study therapy will be considered evaluable. Patients enrolled and/or randomized to therapy but that never receive study therapy will be replaced.

Evaluable for objective response. All enrolled patients who have measurable disease at registration, receive at least 1 cycle(s) of therapy, and have their disease re-evaluated will be considered evaluable for response. These patients will have their response classified according to the definitions stated below. (Note: Patients who exhibit objective disease progression prior to the end of cycle 1 will be considered progressive disease.)

#### 7.1.2 Disease Parameters

Measurable disease. Measurable lesions are defined as those that can be accurately measured in at least one dimension (longest diameter in the plane of measurement is to be recorded) with a minimum size of:

- 10 mm by CT scan (irrespective of scanner type) for studies with a slice thickness of <5mm or twice the slice thickness or MRI

- 10 mm caliper measurement by clinical exam (lesions which cannot be accurately measured with calipers should be recorded as nonmeasurable)
- 20 mm by chest X-ray (if clearly defined and surrounded by aerated lung)

All tumor measurements must be recorded in millimeters (or decimal fractions of centimeters).

Malignant lymph nodes: To be considered pathologically enlarged and measurable, a lymph node must be ≥15mm in short axis when assessed by CT scan (CT scan slice thickness recommended to be no greater than 5 mm). At baseline and in follow-up, only the short axis will be measured and followed.

Note: Tumor lesions that are situated in a previously irradiated area will only be considered measurable, if they have had subsequent progression by at least 5 mm

Non-measurable disease. All other lesions (or sites of disease), including small lesions (longest diameter <10 mm using CT scan), are considered non-measurable disease. Bone lesions without measurable soft tissue component, leptomeningeal disease, ascites, pleural/pericardial effusions, lymphangitis cutis/pulmonitis, inflammatory breast disease, abdominal masses (not followed by CT or MRI), and cystic lesions are all non-measurable.

Target lesions. All measurable lesions up to a maximum of 2 lesions per organ and 5 lesions in total should be identified as target lesions and recorded and measured at baseline. Target lesions should be selected on the basis of their size (non-nodal lesions with the longest diameter), be representative of all involved organ(s), but in addition should be those that lend themselves to reproducible repeated measurements. If a non-nodal lesion is either not present or is initially measured with longest diameter <10mm as a non-target then grows to ≥10mm after baseline, this lesion then becomes a new target lesion as per irRECIST criteria. The non-nodal longest diameter is then added to the sum of diameters, and patient response is calculated with the new lesion.

Lymph nodes merit special mention since they are normal anatomical structures that may be visible by imaging even if not involved by tumor. Pathological nodes that are defined as measurable and may be identified as target lesions must meet the criterion of a short axis of ≥15mm by CT scan. Only the short axis of these nodes will contribute to the baseline sum. The short axis of the node is the diameter normally used by radiologists to judge if a node is involved by solid tumor. Nodal size is normally reported as two dimensions in the plane in which the image is obtained (for CT scan this is almost always the axial plane; for MRI the plane of acquisition may be axial, sagittal or coronal). The smaller of these measures is the short axis. For example, an abdominal node which is reported as being 20 mm x 30 mm has a short axis of 20mm and qualifies as a malignant, measurable node. In this example, 20mm should be recorded as the nodal measurement. All other pathological nodes (those with short axis ≥10mm but <15 mm) should be considered non-target lesions. Nodes that have a short axis <10mm are considered non-pathological and should not be recorded or followed. A sum of the diameters (longest for non-nodal lesions, short axis for nodal lesions) for all target lesions will be calculated and reported as the baseline sum of diameters. If lymph nodes are to be included in the sum, then as noted above, only the short axis is added into the sum. The baseline sum of diameters will be used as reference to further characterize any objective tumor regression in the measurable dimension of the disease. If a non-target lymph node grows to >15mm after baseline, this node then becomes a new target lesion as per irRECIST. The nodal short axis is then added to the sum of diameters, and patient response is calculated with the new lesion.

Non-target lesions. All other lesions (or sites of disease) including pathological lymph nodes should be identified as non-target lesions and should also be recorded at baseline. Measurements are not required, and these lesions should be followed as 'present', 'absent', or in rare cases 'unequivocal progression' (more details to follow). In addition, it is possible to record multiple non-target lesions involving the same organ as a single item on the case record form (e.g. 'multiple enlarged pelvic lymph nodes' or 'multiple liver metastases').

## 7.1.3 Guidelines for Evaluation of Measurable Disease

All measurements should be recorded in metric notation, using calipers if clinically assessed. All baseline evaluations should be performed as close as possible to the treatment start date and never more than 4 weeks before the beginning of the treatment.

The same method of assessment and the same technique should be used to characterize each identified and reported lesion at baseline and during subsequent follow-up studies. Imaging-based evaluation should always be done rather than clinical examination unless the lesion(s) being followed cannot be imaged but are assessable by clinical exam.

Clinical lesions: Clinical lesions will only be considered measurable when they are superficial and >10 mm diameter as assessed using calipers (e.g. skin nodules). For the case of skin lesions, documentation by color photography including a ruler to estimate the size of the lesion is suggested. As noted above, when lesions can be evaluated by both clinical exam and imaging, imaging evaluation should be undertaken since it is more objective and may also be reviewed at the end of the study.

CT, MRI: CT is the best currently available and reproducible method to measure lesions selected for response assessment. This guideline has defined measurability of lesions on CT scan based on the assumption that CT slice

thickness is 5 mm or less. When CT scans have slice thickness greater than 5 mm, the minimum size for a measurable lesion should be twice the slice thickness. MRI is also acceptable in certain situations (e.g. for body scans).

Ultrasound: Ultrasound is not useful in assessment of lesion size and should not be used as a method of measurement. Ultrasound examinations cannot be reproduced in their entirety for independent review at a later date and, because they are operator dependent, it cannot be guaranteed that the same technique and measurements will be taken from one assessment to the next. If new lesions are identified by ultrasound in the course of the study, confirmation by CT or MRI is advised. If there is concern about radiation exposure at CT, MRI may be used instead of CT in selected instances.

Endoscopy, laparoscopy: The utilization of these techniques for objective tumor evaluation is not advised. However, they can be useful to confirm complete pathological response when biopsies are obtained or to determine relapse in trials where recurrence following complete response or surgical resection is an endpoint.

Tumor markers: Tumor markers alone cannot be used to assess objective tumor response.

#### 7.1.4 Response Criteria

# 7.1.4.1 Evaluation of Target Lesions

Prior to the first PD assessment, patients will be evaluated according the following RECISTv1.1 response:

Complete Response (CR): Disappearance of all target lesions, determined by two separate observations conducted not less than 4 weeks apart. There can be no appearance of new lesions.

Partial Response (PR): At least a 30% decrease in the sum of the longest diameter (LD) of target lesions, taking as reference the baseline sum LD. There can be no appearance of new lesions.

Progressive Disease (PD): At least a 20% increase in the sum of the LD of target lesions (with a minimum absolute increase of 5 mm), taking as reference the smallest sum LD recorded since the treatment started, or the appearance of one or more new lesions.

Stable Disease (SD): Neither sufficient shrinkage to qualify for PR (taking as reference the baseline sum LD) nor sufficient increase to qualify for PD (taking as reference the smallest sum LD since the treatment started).

After the first PD assessment per RECISTv1.1 (=irSD per irRECIST), patients will be evaluated for irPD at least 4 weeks apart according to the following definition:

Immune-related Progressive Disease (irPD): At least a 20% increase in the sum of the LD of target lesions (with a minimum absolute increase of 5 mm), taking as reference the smallest sum LD recorded since the treatment started, or appearance of new lesions since the last evaluation.

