# 2.4 Endpoints Assessment

- 2.4.1 Primary Endpoint Assessment: For the intent-to-treat population the progression-free survival (PFS) rate will be defined as the proportion of patients alive and without radiological or clinical progression (leading to withdrawal from the study) at 4 months and patient replacement as specified in section 5.10.
- 2.4.2 Secondary Endpoint Assessment: Overall response rate (ORR) will be determined as per the combined RECISTv1.1 and irRECIST criteria. The progression-free survival (PFS) will be defined as time from date of treatment to date of radiological or clinical progression (leading to withdrawal from the study), or death from any cause, whichever comes first. PFS1 will be from start of study treatment and will be the primary study endpoint. PFS2 will be from start of 1st line platinum therapy. Overall survival (OS) will be defined from the date of treatment to either date of death or censoring. OS1 will be from start of study treatment. OS2 will be from start of 1st line platinum therapy. Follow-up time will be censored at the date of last disease evaluation. Adverse events and reportable serious events are defined by the study protocol (NCI Common Toxicity Criteria for Adverse Events (CTCAE) v5.0).

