7.1.4.4 Treatment Beyond Progression

Accumulating evidence indicates a minority of subjects treated with immunotherapy may derive clinical benefit despite initial evidence of PD.

Subjects will be permitted to continue study treatment beyond initial RECISTv1.1 defined PD, assessed by the investigator, as long as they meet the following criteria:

- Investigator determined clinical benefit
- Tolerance of study drug
- Stable performance status
- Treatment beyond progression will not delay an imminent intervention to prevent serious complications of disease progression (e.g., CNS metastases)
- Tumor markers are stable/improving, if expressed

A radiographic assessment/ scan should be performed within 4-8 weeks of initial investigator-assessed progression to determine whether there has been a decrease in the tumor size or continued PD (termed irPD). The assessment of clinical benefit should be balanced by clinical judgment as to whether the subject is clinically deteriorating and unlikely to receive any benefit from continued treatment.

If the investigator feels that the subject continues to achieve clinical benefit by continuing treatment, the subject should remain on the trial and continue to receive monitoring according to the Study Calendar (see Table 6.2).

For the subjects who continue study therapy beyond progression, further progression is defined as an additional 20% increase in tumor burden with a minimum 5 mm absolute increase from time of initial PD. This includes an increase in the sum of diameters of all target lesions and/ or the diameters of new measurable lesions compared to the time of initial PD. Study treatment should be discontinued permanently upon documentation of further progression (i.e. irPD).

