#### 11.2 Sample Size and Accrual

The investigators hope to enroll patients after 4-6 months of first line platinum therapy without progression. The sample size of this trial is based on the hypothesis that we will improve upon the expected proportion of patients surviving without progression after 4 months of investigational therapy. We will accrue 32 evaluable patients to this trial. Evaluable patients are compliant with study treatment and observed for progression-free survival events, progression (requiring study discontinuation), death, or lack of events at 4 months. Patients non-complaint with study treatment or lost to follow-up (either not secondary to toxicity) will be replaced. Based on the ABC-02 trial, PFS was estimated at 72% and 60% after 4 and 6 months of first line gemcitabine and cisplatin, similar to the initiation point of our study. PFS was 51% and 32% at 8 and 10 months, similar to the end of the treatment period for the primary outcome assessment in this trial. Using a conditional probability argument, combined with the assumption that patient accrual to this study will follow an approximate uniform distribution over the 4 to 6 months of primary therapy for the patients accrued, we can accept the average of the PFS estimates for each period (4-6 months (66%) and 8-10 months (41.5%)) to correspond to our trial time period. We can then standardize the ABC-02 PFS data so that the 4-6 month estimate is 100% to correspond to the start point for patients in this trial and the estimate for 4 months thereafter, 63% (0.415/0.66). For our trial, we hope to improve the PFS rate from 63% for these patients to 85%. With our proposed sample size of 32 patients this trial will have 80% power to detect this difference significantly, with 5% type 1 error, using a 1sided test

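### irPD, which ends treatment beyond first progression, is measured from the nadir in 7.1.4.1 but from the first PD in 7.1.4.4; stopping can differ by section read, and 4-month PFS too if its event is tied to withdrawal

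*Combined protocol and SAP*

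**What the plan says.** **The stopping event**

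- Section 7.1 allows treatment to continue after a first PD by RECIST v1.1, which is relabelled irSD. Before the patient comes off the trial, irPD "must be confirmed by a follow-up scan at least 4 weeks (within 4-8 weeks) following the initial PD/irSD assessment".
- Section 7.1.4.1 defines irPD as growth of the target sum by 20% or more (and at least 5 mm), "taking as reference the smallest sum LD recorded since the treatment started, or appearance of new lesions since the last evaluation".
- Section 7.1.4.4 says the repeat scan "should be performed within 4-8 weeks of initial investigator-assessed progression", and gives the name irPD to PD that persists on it. For patients who stay on treatment, "further progression is defined as an additional 20% increase in tumor burden with a minimum 5 mm absolute increase from time of initial PD"; new lesions enter through the diameters of the measurable ones. It then says: "Study treatment should be discontinued permanently upon documentation of further progression (i.e. irPD".
- The irPD rows of Table 5 list target PD, non-target PD or any new lesion, without a reference sum. Off-study criterion 5.9.11 refers to confirmed PD, also without one.

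**The primary endpoint**

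- Section 2.4.1 defines the rate as "the proportion of patients alive and without radiological or clinical progression (leading to withdrawal from the study) at 4 months".
- Section 11.2 counts "progression (requiring study discontinuation" among the events.
- Section 11.4 uses combined RECIST v1.1 and irRECIST criteria and does not say which of the two dates the event.
- Section 7.1.6 defines PFS as time to progression, with no mention of confirmation or withdrawal.

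**Imaging.** The Study Calendar (6.2, note 6) says scans "will be assessed every 8 ± 1 weeks".

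**The concern.** Both rules apply after the first RECIST PD, both carry the name irPD, and both end treatment. They differ in two respects: the sum against which growth is measured, and whether a new non-measurable lesion counts. Nothing in the protocol says which governs, so the three sites could read identical scans differently and stop one patient while continuing another.

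The repeat scan for a first PD found at the first assessment also falls before the 4-month landmark. If the primary event is progression that takes the patient off treatment or study, the choice of rule could decide whether that patient counts as a failure. With 32 patients the result can turn on one classification.

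**Working it through.** **1. The plan's own figure.** Inputs from 11.2: n = 32, null 63% (0.415/0.66 = 0.629), target 85%, one-sided 5%. Exact binomial:

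- P(X ≥ 25 | 0.63) = 0.0523, above 5%.
- P(X ≥ 26 | 0.63) = 0.0215, so the cut-off is 26/32.
- Power: P(X ≥ 26 | 0.85) = 0.805.

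The stated 80% power is reproduced.

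**2. The two thresholds.** Let N be the nadir and P the sum at first PD. The repeat sum S is irPD if

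- 7.1.4.1: S ≥ the larger of 1.20 × N and N + 5 mm;
- 7.1.4.4: S ≥ the larger of 1.20 × P and P + 5 mm.

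Where the 5 mm minimum does not bind, the band of opposite classification is 1.20 × (P − N) wide.

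| First PD came from | N (mm) | P (mm) | 7.1.4.1 | 7.1.4.4 | Opposite results for S |
|---|---|---|---|---|---|
| Target growth | 100 | 120 | 120 | 144 | 120 to below 144 |
| Target growth | 100 | 125 | 120 | 150 | 120 to below 150 |
| Target growth | 80 | 100 | 96 | 120 | 96 to below 120 |
| New 10 mm lesion, targets at nadir | 100 | 110 | 120 | 132 | 120 to below 132 |
| New non-measurable lesion or non-target PD, targets at nadir | 100 | 100 | 120 | 120 | none on sums |

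The fourth row adds the new lesion to the sum, as 7.1 and 7.1.2 direct.

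Take N = 100, P = 125 and S = 121. Against the nadir this is +21%, so irPD. Against the first PD it is a decrease of 4/125 = 3.2%, far below the 150 mm threshold.

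Independently of the sums, a new non-measurable lesion on the repeat scan is irPD under 7.1.4.1 but does not enter the 7.1.4.4 calculation.

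**3. Timing.** A first scan at week 8 ± 1 plus 4 to 8 weeks puts the repeat scan between 7 + 4 = 11 and 9 + 8 = 17 weeks. Four months is 4 × 30.4375/7 = 17.4 weeks, so the conflict can act before the landmark. A first PD at the second scan (7 + 7 = 14 weeks at the earliest) would be re-scanned at 14 + 4 = 18 weeks or later. Only first-scan progressors are exposed.

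**4. Does the primary endpoint move?**

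- *Event is progression tied to withdrawal or discontinuation* (2.4.1 with the qualifier covering radiological progression; 11.2). A patient in the band fails before 4 months under 7.1.4.1 and can be progression-free under 7.1.4.4.
- *Event is first RECIST PD* (7.1.6; 2.4.1 and 11.4 with the qualifier covering clinical progression only). The patient has already failed at weeks 7 to 9, whichever irPD rule is used. Only the stopping decision differs.

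**5. Illustrative size on the first reading.** The documents give no reclassification rate, so k below is an assumed average number of patients out of 32. The cut-off stays at 26/32.

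| k | False-positive rate, p = 0.63 + k/32 | Power if 85% holds only under the first-PD reference, p = 0.85 − k/32 |
|---|---|---|
| 0 | 2.2% | 80.5% |
| 1 | 4.8% | 64% |
| 2 | 9.7% | 47% |
| 3 | 17.9% | 31% |

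One patient turns 25/32 (p = 0.052) into 26/32 (p = 0.022).

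**The case against.** **The two rules may be sequential.** The sentence on the repeat scan in 7.1.4.4 itself calls persisting PD irPD. The further-20% rule comes later, covers patients who continue, and names no scan. On this reading 7.1.4.1 governs confirmation and the 7.1.4.4 rule governs patients then kept on for clinical benefit. A move from 120 to 125 mm could be called irPD under either section. This has force, but the closing sentence of 7.1.4.4 puts the irPD label on the further-20% rule and makes that the permanent stop, so the section uses the term in two senses. The 125 to 121 mm case also remains awkward: it is above the nadir threshold, yet smaller than at first PD.

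**The gap is not constant.** A reader might infer that the 7.1.4.4 threshold is always 1.44 × nadir. That holds only when first PD was a target-sum rise of exactly 20%; for other routes the gap can be smaller or nil.

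**The example needs baseline to count as a possible nadir.** If only on-treatment sums counted, the first on-treatment sum would itself be the smallest and the two target references would coincide at that scan. But then no PD by target growth could occur at the first scan, which is hardly intended.

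**The error rates are assumed.** At k = 1 the rate is still within the nominal 5%. At k = 3, 3 of the 32 × 0.37 = 11.8 failures expected under the null (25%) would have to be rescored. Those failures include deaths and clinical progressions, which this conflict cannot touch, and continuing past first PD requires five conditions in 7.1.4.4. All of this stands, so the figures show sensitivity and are not an estimate.

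**Conclusion.** The contradiction is real and can be read directly from the text: one term that ends treatment has two reference sums and two new-lesion rules, and neither Table 5 nor 5.9.11 resolves it. Its certain consequence is that the stopping decision can depend on the section a site reads. After target-sum growth, the affected repeat sums run from 1.20 × nadir to just below 1.20 × the first-PD sum, where the 5 mm minimum does not bind.

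The effect on the primary endpoint is conditional. A reader might infer that a week-8 progressor is a 4-month failure under one section and a success under the other. The documents do not support that as a general statement: it requires the event to be progression tied to withdrawal, and 7.1.6 and one reading of 2.4.1 and 11.4 make first RECIST PD the event. Nor do they support the inference that the trial's false-positive rate is 9.7% or 17.9%, since those values rest on assumed counts.

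Confidence is high for the textual conflict and moderate at most for an effect on the 4-month rate.

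**What to change.** 1. Reconcile 7.1.4.1 and 7.1.4.4 to one irPD definition with one reference sum and one rule for new measurable and non-measurable lesions, and settle whether persisting PD on the repeat scan is irPD. Have Table 5 and 5.9.11 cite that definition. Which rule should govern stopping of treatment is for the sponsor to decide.
2. Separately, state in 2.4.1 and 11.4 whether the 4-month PFS event is first RECIST PD or irPD, and align 7.1.6 and 11.2. Pointing 11.4 to the irPD definition alone would settle this question without saying so.
3. Report the 4-month rate under the other definition as a sensitivity analysis, using collected lesion measurements where the needed scans exist. The Study Calendar shows no scans at the end-of-treatment visit or in follow-up, so a patient stopped under the stricter rule may lack the later scan that the other rule needs. State how many patients this affects.

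The cost is protocol wording and one extra derivation. The downside is that the rate may be slightly less favourable under one definition.
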